### Research Questions and Hypotheses:

*Specific Aim 1: To determine the impact of service dogs and determine who benefits the most.*

**Hypothesis 1A:** Individuals partnered with SDs will have greater improved mental health over time (Primary outcome will be the PCL checklist. Secondary mental health will be quantified by scores on depression and alcohol use).

**Hypothesis 1B:** Individuals partnered with SDs will have improvements over time in secondary factors of physical, psychosocial, and socioeconomic variables. The secondary factors are defined as follows: 1) physical factors: co-morbidities, medication use, sleep 2) psychosocial factors: community participation, quality of life and 3) socioeconomic factors: demographic and health care utilization and out-of-pocket health care expenses.

*Specific Aim 2: To determine costs associated with total health care utilization and mental health care utilization among Veterans with mental health disorders needs and service or therapy dogs.*

**Hypotheses 2A:** Individuals partnered with SDs will have decreased mental health care utilization over time.

**Hypotheses 2B:** Individuals partnered with SDs will have decreased total health care utilization over time.

*Specific Aim 3: To determine recommendations for providing service dogs to Veterans.*

Develop a strategic plan to provide service dogs to Veterans. A consensus meeting will be planned and will include all investigators of the project along with key individuals from funding agency to discuss findings of study.

*Secondary Aim:* To compare study findings to another VA funded study that is providing dogs as pets to Veterans with PTSD. Both studies are using similar measures to assess mental and psychosocial factors. Data will be compared across groups (SD to dog as a pet) to determine if the highly trained dogs help the Veteran more than having a dog as a pet.

*Projected Time Table*

Training of SDs is time intensive and expensive, with limited numbers of dogs who actually graduate. We will work with vendors to obtain the dogs, but recognize that there may be a significant waiting period prior to pairing. To demonstrate maximum treatment benefits, the data collection phase of this three-year study will be conducted for a minimum 18 months (maximum of 24 months for early enrollees) as we feel the acclimation period for the human-animal bond is longer than 18 months. This allows sufficient time for statistical analyses.

*Timeline*

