### **Research Design and Methods**

#### *Design*

This 3-year, mixed methods modified, non-randomized trial will follow individuals for two years. Due to the inability to recruit veterans interested in participating in a control (no dog) group, this group has been eliminated going forward with the study. The study will examine the influence of SDs by assessing the longitudinal change in mental health assessment over time among veterans who have PTSD. The group will consist of individuals partnered with SDs. Following initial screening for inclusion criteria, including criteria set by dog vendors, subjects who are eligible will receive a SD. This study will measure changes over time in the primary outcome of mental health. Additional outcomes in psychosocial health and healthcare utilization will be included. Recruits successfully completing the screening process will be placed on a vendor's waiting list to receive a SD upon the dog's completion of training. Recruits who do not meet all criteria, including vendor criteria, will be ineligible to participate..

Data will be collected at baseline and at 3, 6, 9, 12, 18 and 24 months for individuals with service dogs. For those awaiting service dogs, repeated assessments will occur every 3 months until obtaining a SD. Once baseline data has been collected for 24 months, assessments will occur every 6 months until the Veteran is paired with a SD. Baseline data will include detailed information on the characteristics of the participants, their mental health, psychosocial well-being, socioeconomic and healthcare utilization characteristics. As we want to obtain information regarding the changes in health and wellbeing over time, a prospective study will permit this type of comparison.

*Sample:* The study will use a convenience sample of VHA patients who are currently in treatment for PTSD. We have chosen to use these criteria as a safety measure for the veteran and the dogs. At this time, there are currently 600 veterans receiving care at James A. Haley VAMC for PTSD, with an estimated 25 new veterans seen in the clinic per week. We are confident that an adequate number of Veterans will be recruited for the study. We will monitor recruitment and retention numbers on a monthly basis. The use of additional VA hospitals as a potential source for recruitment is the contingency plan should we be unable to meet enrollment numbers.

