Training of SDs for a specific individual takes time, and immediate placement of a dog with a Veteran most likely will not occur. Thus, baseline data collection will occur at the time of consent and every three months until the dog becomes available for the Veteran. If a Veteran completes 24 months of observation and is still not paired with a dog, assessments will continue every 6 months until a dog becomes available. If the Veteran is not been paired by 48 months they will be withdrawn from the study. Through observations and questionnaires we will ask the Veteran about how they feel, their mood, and their quality of life. During the waiting period, Veterans will be required to take an education course related to dog care and responsibility of dog ownership. This course will be provided by the study team and will be online through CITI or via paper copy. A paper copy of the Education Modules in the course will be provided to Veterans as a reference. Course content will cover all aspects of Service Dog ownership including grooming, health maintenance, and financial responsibility. A competency test will be given at the end of the course to ensure Veterans understand the material. If the Veteran fails to pass the test with a score of 80% or better, remedial training will be given by the study team and the test will be re-taken until passed. A Veteran Guide for Veterinary Care information sheet will be provided at this time as well. This Guide will contain information about health maintenance and when to take the dog to the veterinarian.

Once the study team receives word from a vendor that a SD is about ready for pairing, the Veteran and vendor will have an opportunity to talk to ensure that an appropriate match will be made. When the dog is ready, the Veteran will be required to travel to the vendor location. Travel may be by air or car, depending on the vendor location and considering the Veteran's preference when possible. If a Veteran drives their personal vehicle, he/she will be reimbursed at the government mileage rate upon completion of training and return home. Vendor staff will make travel and lodging arrangements for the Veteran. Lodging, air travel, and meals will be paid for by the vendor during the pairing (per Federal regulations) and reimbursed by VA per the SOW. The pairing process may vary by vendor and can last from one to three weeks.

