We expect some individuals to benefit more than others. We hypothesize that individuals with greater limitations will have the most improvement when provided with an SD. Consequently, we will conduct a sub-analysis of the SD group. We acknowledge this is an exploratory analysis and the power is limited. The hypothesis we will test is individuals who score lower in psychosocial factors (e.g. community participation) at baseline will show greater improvements in those characteristic than individuals who scored higher. Therefore we will use the subcomponents scores of continuous measures and dichotomize them at a clinically meaningful point (e.g.,  $\geq 80 \geq 75^{\text{th}}$  percentile) at the baseline measure. All individuals will be put into one of two groups based on this cutpoint. Repeated measures analyses will be completed on all continuous variables with the between factor being the two groups and the within measure equaling variables of physical, psychosocial and economic characteristics.

In addition, we will conduct an exploratory analysis to determine whether relationships exist between group status (SD vs. control), demographic variables (age, gender, living arrangements, marital status, etc.) and the outcomes of interest – mental health (, PCL-C) and psychosocial factors (e.g. community participation). Categorical demographic variables will be analyzed using a chi-square for variables that are dichotomous, and one-way ANOVAs will be used for continuous variables that have multiple categories. Continuous demographic variables (e.g., age) will be compared to the outcomes using correlations: Pearson for normally distributed variables and Spearman rho for not-normally distributed variables. Sub-analysis will examine the relationship between the outcomes of interest and the physical, psychosocial and economic variables. Correlation analysis will be used to determine significant relationships. Two separate multiple regression models will be developed using any variables significant at a  $p$ -value  $< 0.10$  in the univariate analysis. The outcomes will be from the 18-month visit, whereas the predictor variables will be those recorded at baseline. These analyses will be used to describe those characteristics of Veteran's most likely to benefit from obtaining a SD compared to control subjects.

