### *4.0 Human Subjects*

#### *1. Risk to Subjects*

- Human subject involvement and characteristics: Subjects will be asked to participate in this study for approximately two years which includes a screening visit, multiple baseline data collection pre intervention and additional follow up sessions at 3, 9, 12, 18, and 24 months. As described in the methods section, all subjects will be Veterans who are in treatment for PTSD at the Tampa VA. Inclusion/exclusion criteria is described in the methods section. All Veterans will be accepted into the study regardless of race and/or gender.

- Sources of Materials: Research material will be obtained from the subject's electronic medical record as well as data collected from the individual subjects. The data will be obtained specifically for research purposes.
- Potential Risks: This study is a minimal risk study. Subjects are required to complete questionnaires over 2 years.

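### The exploratory low-versus-high baseline split can produce its own hypothesised result through regression to the mean; how often depends on which pre-pairing scores are used and on a correlation the plan does not give

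*Combined protocol and SAP*

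**What the plan says.** **The sub-analysis.** Under Data Management and Statistical Analysis, Hypothesis 1B, the plan takes the service-dog group alone and hypothesises that "individuals who score lower in psychosocial factors (e.g. community participation) at baseline will show greater improvements in those characteristic than individuals who scored higher". Subscores are cut at a clinically meaningful point on the baseline measure, with a 75th percentile among the examples. "All individuals will be put into one of two groups based on this cutpoint". A repeated-measures analysis then uses these two groups as the between factor. The plan adds: "We acknowledge this is an exploratory analysis and the power is limited".

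**Comparator.** The Design section says of the no-dog control group that "this group has been eliminated going forward with the study".

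**Baseline.** The Screening Visit paragraph describes one set of baseline questionnaires. Elsewhere the word covers the whole waiting series:
- Participant Recruitment and Informed Consent: "baseline data collection will occur at the time of consent and every three months until the dog becomes available for the Veteran".
- Design, on when assessments become six-monthly: "Once baseline data has been collected for 24 months".
- Human Subjects, Risk to Subjects: "multiple baseline data collection pre intervention".

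**Adjustment.** The general Analysis paragraph has a rule that differences found at baseline will be adjusted for later. The one baseline outcome score named as a covariate is the PTSD Checklist, under Hypothesis 1A.

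**The concern.** The score that forms the groups is also the outcome. Unless repeated scores correlate perfectly, Veterans chosen for a low score tend to score higher next time, and those chosen for a high score tend to score lower, with or without a dog. That drift is in the direction the plan hypothesises, and with no comparator it cannot be told from a real difference in benefit. The limited-power caveat does not cover it: low power means missing a real effect, whereas this is a false positive that becomes more likely as N grows.

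Finding out who benefits most is part of Specific Aim 1, and Specific Aim 3 is to make recommendations on providing dogs. A spurious finding that the most limited Veterans gain most could feed into both.

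**Working it through.** The plan gives no sample size, power or error rate for this sub-analysis, so there is no figure to reproduce. The check asks how often the hypothesised result appears when the dog has no effect.

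**Inputs**
- N = 187, from 220 enrolled less 33 drop-outs (Sample paragraphs, which also state 200 completers); N = 65, from the Hypothesis 1 power paragraph.
- Six follow-ups: 3, 6, 9, 12, 18 and 24 months (Design).
- Significance level 5% (Analysis).
- Correlation between assessments: not given for this analysis. Four values were tried: first-order autoregressive, AR(1), 0.80, borrowed from the power calculation in the Sample paragraphs, with one step per visit; and constant 0.80, 0.90 and 0.96. The 0.80 and 0.90 constants are assumptions. The 0.96 is the test-retest value quoted for the Community Integration Questionnaire, an optimistic bound over 24 months.
- Cut at the 75th percentile (assumed); normal scores; no mean change.

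**Expected spurious gap, one score in both roles**

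For a standard normal score cut at q = 0.674, with density φ(q) = 0.318, the group means differ by φ(q)/0.25 + φ(q)/0.75 = 1.271 + 0.424 = 1.695 SD. At a follow-up with correlation ρ to baseline, the low group's excess gain is (1 − ρ) × 1.695 SD:
- ρ = 0.80: 0.20 × 1.695 = 0.34 SD.
- ρ = 0.90: 0.10 × 1.695 = 0.17 SD.
- ρ = 0.96: 0.04 × 1.695 = 0.07 SD.
- AR(1) 0.80 at month 18 (fifth follow-up): ρ = 0.80⁵ = 0.328, so 0.672 × 1.695 = 1.14 SD.

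**Expected gap, split on consent score and change from last pre-pairing score**

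The gap is (ρ from consent to last pre-pairing − ρ from consent to follow-up) × 1.695 SD. Under constant correlation it is zero. Under AR(1) 0.80 with m waiting assessments it is 0.80ᵐ × (1 − 0.80⁵) × 1.695 at month 18:
- m = 1: 0.800 × 0.672 × 1.695 = 0.91 SD.
- m = 4: 0.410 × 0.672 × 1.695 = 0.47 SD.
- m = 8: 0.168 × 0.672 × 1.695 = 0.19 SD.

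**Expected gap, mean of n scores in both roles, constant correlation**

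The mean has variance v = ρ + (1 − ρ)/n, and the gap is 1.695 × [(1 − ρ)/n] / √v. For ρ = 0.80 and n = 4, v = 0.85 and the gap is 1.695 × 0.05 / 0.922 = 0.09 SD, against 0.34 SD for a single score.

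**Simulated false-positive rates** (Hotelling group-by-time test on change, nominal 5%)

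| Splitting / reference score | N | AR(1) 0.80 | Const. 0.80 | Const. 0.90 | Const. 0.96 |
|---|---|---|---|---|---|
| One score, both roles | 187 | 100% | 91% | 58% | 20% |
| One score, both roles | 65 | 87% | 41% | 19% | 10% |
| Mean of 4, both roles | 187 | 100% | 23% | 12% | 7% |
| Mean of 4, both roles | 65 | 77% | 9% | 7% | 6% |
| Consent / last pre-pairing, 1, 4, 8 waits | 187 | 100, 47, 11% | 4–6% | 4–6% | 4–6% |
| Consent / last pre-pairing, 1, 4, 8 waits | 65 | 59, 15, 6% | 3–6% | 3–6% | 3–6% |

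Repeat runs agree to within about 4 points; the 0.96 case with one score at N=187 ranged from 20% to 24%. With one score in both roles, nearly all rejections (94% or more) were in the hypothesised direction.

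A Geisser-Greenhouse corrected test at N=200, counting only results in the hypothesised direction (nominal about 2.5%), gave about 100%, 92%, 60% and 25% for one score in both roles. At N=65 it gave 96% for AR(1) 0.80 and 37% for constant 0.80.

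**The case against.** **The plan need not use one score twice.** Splitting on the consent score and measuring change from the last pre-pairing score is equally open, and under constant correlation the problem then disappears. This stands. That reading is not stated, however, and it does not protect if the correlation decays and the wait is short.

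**The high rates rest on a borrowed correlation.** This also stands. For the plan's own example, community participation, the only documented value is 0.96, which gives about 20% at N=187 and 10% at N=65. A reader might infer from the 100% figure that a false result is certain. The documents do not support that, because the true correlation pattern is not given. Equally, test-retest reliability is not stability over two years, so 0.96 is not a safe estimate.

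**The general rule on baseline differences might cover it.** Groups cut on a score differ on it by construction, and adding that score as a continuous covariate held the two-sided error at month 18 to about 4–7%. But the plan does not say the rule reaches the splitting score, and such adjustment would absorb much of the question being asked.

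**It is exploratory.** True, and it is one of several analyses on who benefits; the same section also has a predictors-of-success regression and 18-month regressions. That limits the severity but does not remove the bias.

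**Conclusion.** The concern holds in a bounded form. When one pre-pairing score both forms the groups and anchors change, regression to the mean alone can produce the hypothesised result well above the nominal 5%: from 20% to about 100% at N=187, and from 10% to 87% at N=65, over the correlations tried. These figures assume a 75th-percentile cut, six follow-ups, normal scores and no mean change.

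The size depends on three things together: the correlation pattern, N, and which assessments serve as splitting and reference scores. A reader might infer that the loose use of the word baseline is the sole driver. It is not. Under AR(1) 0.80 at N=187 the rate stays near 100% for a single score and for a mean of four, while under constant 0.80 it falls from 91% to 23%. Averaging helps only if the correlation does not decay.

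Nor do the documents support reading this as a threat to the main result. The primary PTSD Checklist analysis is unaffected, and outcomes other than the splitting score are less affected. Severity is minor to moderate.

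**What to change.** **Recommended, and sufficient alone.** State which pre-pairing assessment forms the groups and which is the reference for change. Do not test the same-score low/high comparison or report it as evidence that more limited Veterans benefit more. Show it descriptively, labelled as subject to regression to the mean. This changes wording only; the cost is that this exploratory hypothesis has no formal test.

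**Optional, if a test is wanted.** Use the waiting-period assessments as the within-person reference. Model scores after enrolment on enrolment score × time since enrolment, time since pairing, and enrolment score × time since pairing, allowing for repeated measures; the last term is the exploratory test. A simple before/after indicator fits poorly with the plan's statement that "we feel the acclimation period for the human-animal bond is longer than 18 months", so the time-since-pairing term should be gradual or in categories.

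The costs need stating beside any result:
- Power is low. For an interaction of 0.2 SD per SD building up to 18 months, least squares gave 7–46% at N=187 and 9–20% at N=65. It reached 15–86% at N=187 only with the covariance modelled correctly.
- At N=65 the test is liberal (6–12%), so it needs a small-sample correction.
- It depends on an assumed effect shape, on nothing else changing at pairing, and on waiting times the plan calls unknown. The simulated waits stopped at 24 months, whereas the plan allows up to 48.

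**Separate wording point.** The 18-month regressions are still described as showing who benefits relative to controls. With no control group left, delete that clause and call them prognostic.

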### Other Forms

Form	Purpose	When Completed	Who Completes
Home environment checklist	Checklist to assess home environment prior to dog placement	Pre-pairing home visit	Study Team Dog Trainer
Dog Care Test	Test knowledge of dog care and responsibility	After completion of Dog Care Course	Veteran
Service Dog Post Pairing Evaluation	Assess pairing and identify potential health or behavior problems in dogs	One week post pairing, months 1, 2, 3, 6, 9, 12, 18, 24	Study Team Dog Trainer at home visit
Veterinarian Checklist	Assess dog's health	Once per year	Veterinarian caring for each dog
Veteran Guide for Veterinary Care	Provides information to Veteran about maintain dog's health	Provided when Dog Care Course is completed	Information provided to Veterans
Home visit information sheet	Provides information to Veterans about how and why the home visit is done	Provided after IC, prior to home visit	Information provided to Veterans

Service Dog Questions	Veteran's subjective report about the dog's behavior and Veteran's satisfaction with the dog	Months 3, 6, 9, 12, 18, 24	Study team member present at home visit
-----------------------	--	----------------------------	---

Unless otherwise noted, all measures are completed at all visits.

\*\*Data for these items will be abstracted from medical record

Mental Outcomes: Outcomes for the main hypotheses will be measured with the following measure using the PTSD Checklist (PCL). PTSD Checklist is a 17-item self-report measure of the 17 DSM-IV symptoms of PTSD. Respondents rate how much they were “bothered by that problem in the past month”. Items are rated on a 5-point scale ranging from 1 (“not at all”) to 5 (“extremely”). The PCL can be scored in several different ways. A total score (range 17-85) can be obtained by summing the scores from each of the 17 items. Although the CAPS was used initially for the study, it was decided by the research team with input from the funding agency that diagnosis of PTSD will be confirmed by referring clinician and eliminate stress of completing the interview for the veteran. For some of the veterans that are enrolled in the study, CAPS is available in their medical record. If it is available, we will abstract the information to further confirm the diagnosis.

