*Alcohol Use Disorder Identification Test (AUDIT-C) and/or Addiction Severity Index –Alcohol Use Disorders Identification Test (AUDIT)-C is a 3-item paper and pencil alcohol screen to identify hazardous drinking or those with problematic alcohol consumption use (abuse and dependence). There is a five-point scale ranging from 0 to 4. The items are summed to obtain a total score ranging from 0-12. For men, a score of 4 or more is considered positive. For women, a score of 3 or more is considered positive. Internal consistency reliability has been reported as 0.80.*

Physical factors: Physical factors will include items that can be drawn from the medical record (co-morbidities, medications). Abstracting medical record data at least one year prior allows for an evaluation of trends or sudden departures from normal care or medication profiles. *In addition, we will track the number of visits and type of therapies that the subjects will be participating in while in treatment for their PTSD.*

*Pittsburgh Sleep Quality Index (PSQI) is a 24 item self-administered survey used to assess sleep-related problems during the past month. The first 19 items are completed by the subject and there are five items completed by a bed partner or roommate. The five items answered by a bed partner or roommate are used as clinical information and are not included in scoring. The first 19 items are grouped into seven components (sleep quality, sleep latency, sleep duration, habitual sleep efficiency, sleep disturbances, use of sleep medication, and daytime dysfunction) each weighted equally on a 0-3 scale. The seven component scores are then summed to yield a global score, which has a range of 0-21; higher scores indicate worse sleep quality. The seven component scores of the PSQI had an overall reliability coefficient (Cronbach's  $\alpha$ ) of 0.83. We will also be using the PSQI-A, addendum for PTSD. The PSQI-A asks an additional ten questions that target PTSD-related sleep problems.*

Psychosocial factors:

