*Community Integration Questionnaire (CIQ)* consists of 15 questions focusing on community integration behaviors. The CIQ is used to assess integration behaviors in the home, in social settings, and in productive activities such as employment and education. Items are scored on a 0-2 scale and scores can range from 0-29. A high score indicates greater independence and better community integration. The CIQ has been reported to have excellent internal consistency (Chronbach's  $\alpha = 0.76$ ) and test-retest reliability (0.96).

*Health Related Quality of Life will be assessed by the SF12.* This is a subset of the SF-36, a generic health status measure that has been shown to be valid and reliable in a wide variety of health care settings.

Socioeconomic Factors: Factors of socioeconomic status will include items related to demographics (e.g. age, gender, marital status) and economic items which will include years of education, type of employment and occupation, income (self and household), type of health insurance carried, and number of individuals living in household.

Healthcare utilization: will encompass out of pocket expenses, and asks number of visits to health professionals over the past year (an average per month will be determined), average annual out-of-pocket healthcare expenses, current prescription medication used, etc.

*Data Management and Statistical Analysis*

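### The example cut-point in the sub-analysis of Veterans with greater limitations does not isolate the most limited Veterans on the participation scale, and no cut or direction is set per scale

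*Combined protocol and SAP*

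**What the plan says.** The sub-analysis is described under Hypothesis 1B in Data Management and Statistical Analysis. Its premise is: "We hypothesize that individuals with greater limitations will have the most improvement when provided with an SD". The hypothesis to be tested is that "individuals who score lower in psychosocial factors (e.g. community participation) at baseline will show greater improvements" than those who start higher. The method follows: "Therefore we will use the subcomponents scores of continuous measures and dichotomize them at a clinically meaningful point", with ≥80 ≥75th percentile given as an example and no connecting word between the two figures. Then: "All individuals will be put into one of two groups based on this cutpoint". The two groups become the between-subject factor in repeated measures analyses of all continuous variables, covering physical, psychosocial and economic characteristics. The plan adds: "We acknowledge this is an exploratory analysis and the power is limited".

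Table 2 assigns community participation to the CIQ. The section on measurements gives these ranges and directions:

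- CIQ: "Items are scored on a 0-2 scale and scores can range from 0-29"; a high score is better.
- Pittsburgh Sleep Quality Index (PSQI) global score: "which has a range of 0-21; higher scores indicate worse sleep quality".
- PTSD Checklist (PCL): "A total score (range 17-85) can be obtained by summing the scores from each of the 17 items"; items run from not at all bothered to extremely bothered, so high is worse.
- AUDIT-C: 0-12, with a positive screen at the upper end, so high is worse.

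No range or direction is given for the SF12 or the PHQ-9.

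**The concern.** The hypothesis is about the Veterans who start worst off, but the example cut is an upper one. Where high is better, an upper cut separates the best-off Veterans from everyone else. The group that stands for greater limitation is then most of the sample. Where high is worse, the same cut separates the worst-off, but a hypothesis worded in terms of lower scorers points at the wrong side of it. No sentence says which side counts as more limited on which scale.

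Specific Aim 1 asks who benefits most, and Specific Aim 3 uses the findings to recommend how dogs should be provided. A result labelled as applying to the more limited should describe those Veterans, and the split should be settled before the data are seen.

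**Working it through.** The plan gives no sample size, power or fixed cut for this sub-analysis, so there is no figure to reproduce. The check compares the example cut with the plan's own scale descriptions.

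**1. Can a score of 80 occur?** The stated maxima are CIQ 29 (15 items × 2 = 30 by arithmetic), PSQI 21, AUDIT-C 12 and PCL total 85. Since 80 exceeds 29, 30, 21 and 12, a raw cut of 80 leaves nobody in the upper group on the first three scales. A subcomponent cannot exceed its total, so using subcomponents does not help. On the PCL total, 80 lies (80 − 17)/(85 − 17) = 63/68 = 93% of the way up the range, a mean item score of 80/17 = 4.7 out of 5. Read as a percentile, 80 is attainable and splits the sample into one fifth and four fifths. The 75th percentile is always within range.

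**2. Who falls where on the CIQ?** With a ≥75th-percentile cut, the upper group is the least limited quarter and contains none of the most limited quarter. The lower group is 75% of the sample, and the most limited quarter makes up 0.25/0.75 = one third of it.

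| Veterans | Upper group | Lower group |
|---|---|---|
| 220 (maximum recruited) | 55 | 165 |
| 200 (stated expected completers) | 50 | 150 |
| 187 (220 less the stated 33 drop-outs) | 47 | 140 |

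With an 80th-percentile cut, 0.20/0.80 = one quarter of the lower group is in the most limited fifth.

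**3. How limited is the lower group?** Assume normal scores. The 75th percentile is q = 0.674, with density φ(q) = 0.318.

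- Everyone below the 75th percentile: mean = −0.318/0.75 = −0.42 SD.
- A true lowest quarter: mean = −0.318/0.25 = −1.27 SD.
- For the 80th percentile, the same calculation gives −0.35 SD, against −1.40 SD for the lowest fifth.

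**4. What does this do to the comparison?** The distance between the two group means is 1.27 + 0.42 = 1.69 SD whichever tail is cut. If extra improvement rises in a straight line with limitation, both splits therefore expect the same difference. If an extra improvement Δ is confined to the most limited quarter, the lower-tail split shows Δ and the upper-tail split shows Δ/3.

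The detectable difference (two-sided 5%, 80% power) is d = (1.960 + 0.842) × √(1/n₁ + 1/n₂). For 50 against 150 this is 2.802 × 0.163 = 0.46. With 187 Veterans it is 0.47. The tail chosen does not change it. A median split of 200 gives 0.40.

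**5. Scales where high is worse (PCL, PSQI, AUDIT-C).** The ≥75th-percentile group is exactly the most impaired quarter. If lower scorers are taken as the more limited, as the hypothesis is worded, the milder 75% receive that label.

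**The case against.** The strongest reply has four parts.

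- **The cut is only an example.** The commitment is to some clinically meaningful point, in an analysis the plan calls exploratory and low in power. This stands, and it limits the weight of the point. But it is the only guidance given, and it does not suit the construct the plan itself names.
- **80 need not be a raw score.** The two figures stand side by side without a connector. They could be two percentiles, or a remnant of editing or of text extraction. This also stands. A reader might infer that the split is impossible because one group is empty. The documents support that only under the raw-score reading. The percentile reading has its own problem on the CIQ.
- **The hypothesis concerns psychosocial factors.** Table 2 lists only the SF12 and CIQ scales there, with the PCL and AUDIT-C under mental outcomes and the PSQI under physical factors. The labelling problem on those scales therefore arises only if the rule is extended to them. The plan leaves that open: it refers to all continuous variables and to physical characteristics, and elsewhere under Hypothesis 1B it counts depression as psychosocial.
- **Below against above the 75th percentile still compares lower with higher scorers.** True, and under a straight-line relation nothing is lost on average. What is lost is a group that represents the most limited, and the sharpness of the contrast if the benefit is concentrated there.

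A reader might also infer that the upper cut runs the wrong way on scales where high is worse. It does not. On those scales it captures the whole most impaired quarter, and only the wording about lower scorers would misfit.

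**Conclusion.** The point holds in a limited form. On the CIQ, the plan's example puts three quarters of the sample in the group meant to represent greater limitation. That group averages about −0.42 SD, against −1.27 SD for the true lowest quarter, and only one third of it belongs to that quarter. The shares follow from the percentile alone; the SD figures assume normal scores. The cost to the comparison ranges from nothing (straight-line relation) to a threefold dilution (extra benefit confined to the most limited quarter).

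No scale has a stated cut or a stated more-limited side. A sample percentile also depends on who enrols, so it is not in itself clinically meaningful.

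The documents do not support reading this as a failure of Specific Aim 1. The analysis is exploratory, and the plan also has regressions for predictors of success and of 18-month outcomes on baseline characteristics. Those do not formally test baseline severity as a modifier, but they address the same question.

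**What to change.** Amend the sub-analysis text before the data are analysed:

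- Delete ≥80.
- Define the target group as *more impaired at baseline* in place of the wording about lower scores.
- Make the main sub-analysis a baseline-score-by-time interaction, with baseline score as a continuous modifier, so that no cut is needed.
- If a split is also shown, use the most impaired quarter on each scale: lowest quarter of the CIQ; highest quarter of the PSQI, PCL and AUDIT-C. The sponsor should confirm the direction of the SF12 and PHQ-9 first, because the documents do not state it.
- Call the split a sample quartile, not a clinically meaningful point.

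The cost is wording in the analysis plan. No new data are needed. A quarter split from the other tail has the same detectable difference (d about 0.46 with 200 Veterans). One separate limitation remains under either form: without a control group, Veterans who start worst tend to drift towards the mean, so the result should stay descriptive.
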